2.0	07-NOV-2018	
Version 2 includes one change. In the Secondary Objective analysis methods, the following sentence was added "H(1), H(2) and H(3) denote the null hypothesis for change in AFEQT, change in SF-12 mental component, and SF-12 physical component.". This sentence was added based on FDA Study design consideration from FDA STOP Persistent AF IDE approval letter dated November 11, 2016.
	
[name], Sr. Principal Statistician, CRHF

3.0	15-NOV-2018	
Version 3 of the SAP defines an interim analysis. The addition of the interim analysis was suggested by the FDA in feedback on Q181709 dated October 17, 2018. The interim analysis methods have been added to Appendix A.
 
An interim analysis was not previously included in SAP version 1 and 2 or the study protocol. Interim primary efficacy and primary safety objectives and statistical performance criteria have been defined.
 
The interim analysis plan also includes all secondary and ancillary objectives for the study. Due to interim follow-up, some of the objectives have been modified to account for interim this (ie. not all subjects will have complete 12 month data).
 
The intent of the version is to pre-defined all objectives and analyses (interim primary efficacy and primary safety, secondary and ancillary) that will be reviewed during an interim analysis.
 
The timing of this interim analysis will occur when at least 70% of follow-up has occurred. This timing is projected to coincide with the projected last 6-month visit date. It is estimated that 75% of the total expected follow-up will be available at the timing of this analysis.
 
Appendix A has been added and includes all the details of the interim analysis.
 
Additional changes include three new defined subgroups:
 
 Subjects with symptomatic persistent AF documented by two documented ECGs versus subjects with symptomatic persistent AF documented by one ECG and a doctor note indicating the patient had symptoms consistent with AF Subjects with body mass index (BMI) > 40 versus ≤ 40. 	
[name], Sr. Principal Statistician, CRHF

STOP Persistent AF Statistical Analysis Plan

08-JUL-2019

Version 4.0

Page 4 of 25

Medtronic

Version	Date	Summary of Changes	Author(s)/Title
		
Both subgroups have been added to assess changes in inclusion and exclusion criteria between clinical investigational plan version 5 to version 6.
 
3. Subjects with baseline ECG performed within 30 days of index ablation versus > 30 days.
 
This subgroup has been added to address the FDA study design consideration in FDA approval letter dated January 10, 2018.
	
4.0	08-JUL-2019	
Removed the interim analysis defined in version 3 as well as Appendix A, which specifies the interim analysis.
 
Reverted back to version 2, except for the additional three pre-specified subgroup analyses defined in version 3, per FDA feedback.
 
Per FDA feedback, added a sensitivity analysis (section 6.2.4.3) to the secondary objective to assess the effect of missing data on QoL outcomes.
 
Added additional clarifications about subgroup and pooling analyses in section 6.3.
 
Removed references to European study centers.
	[name], Principal Statistician, CRHF

2. List of Abbreviations and Definitions of Terms

Abbreviation	Definition
AE	Adverse Event
AF	Atrial Fibrillation
AF/AFL/AT	Atrial Fibrillation, Atrial Flutter or Atrial Tachycardia
AFEQT	Atrial Fibrillation Effect on QualiTY-of-life assessment
CBA	CryoBalloon Ablation
CIP	Clinical Investigation Protocol
LTFU	Lost To Follow-Up; alternatively, Loss To Follow-Up
MedDRA	Medical Dictionary for Regulatory Activities
PMA	Pre-Market Approval
PMA-S	Pre-Market Approval Supplement
PMDA	Pharmaceuticals and Medical Devices Agency
PNI	Phrenic Nerve Injury
QoL	Quality of Life
SAP	Statistical Analysis Plan
SF-12	Medical Outcomes Short Form-12
SoC	Standard of Care

3. Introduction

The purpose of the Statistical Analysis Plan (SAP) for the STOP Persistent AF study is to provide pre-analysis documentation and rationale for the statistical procedures used in planned analyses which are performed throughout the investigation. Specifically, this plan outlines methods employed in the study's Pre-Market Approval (PMA) submission and final report, as well as in any planned publications. It does not limit the analysis that will be completed, as further analysis beyond what is specified in this document is likely.

This SAP was developed based on version 5 of the STOP Persistent AF Clinical Investigation Protocol (referred to as the CIP in this SAP), dated 17/APR/2017. Topics included in this document which are not included in the CIP are handling of missing data (section 6.4), subgroup analyses (section 6.7), and validation requirements (section 8).

4. Study Objectives

4.1. Primary Efficacy Objective

Demonstrate an acceptable efficacy success rate at 12 months after the pulmonary vein isolation (PVI) ablation procedure.

4.2. Primary Safety Objective

Demonstrate an acceptable safety profile of the pulmonary vein isolation (PVI) ablation procedure.

4.3. Secondary Objective

Demonstrate an improvement in quality of life between baseline and 12 months after the index ablation procedure as measured by the AFEQT and SF-12 questionnaires.

4.4. Ancillary Objectives

- [REDACTED]

[figure not shown]
5. Investigation Plan

The purpose of the study is to provide data demonstrating the safety and effectiveness of the Arctic Front Advance and Freezor MAX Cardiac CryoAblation Catheters for the treatment of symptomatic drug refractory persistent AF. The study is proposed by the sponsor as a result of feedback received from the US Food and Drug Administration (FDA) on pre-submission Q151184, regarding a proposal to expand the indications for use for the Arctic Front Advance to include patients with persistent AF. The study is also designed to expand the indication for the Freezor MAX Cardiac CryoAblation Catheter. The proposed indication for the Arctic Front Advance CryoAblation Catheter is as follows: The Arctic Front Advance Cardiac CryoAblation Catheters are indicated for the treatment of drug refractory recurrent symptomatic paroxysmal and persistent atrial fibrillation. The proposed indication for the Freezor MAX Cardiac CryoAblation Catheter is as follows: The Freezor MAX Cardiac CryoAblation Catheters are indicated for use as an adjunctive device in the endocardial treatment of paroxysmal and persistent atrial fibrillation in conjunction with the Arctic Front Advance Cardiac CryoAblation Catheter for the following uses: gap cryoablation to complete electrical isolation of the pulmonary veins, cryoablation of focal trigger sites and creation of ablation line between the inferior vena cava and the tricuspid valve. A sub-study [REDACTED]

[REDACTED]

Medtronic, Inc. is sponsoring the STOP Persistent AF Study; a prospective, interventional, multi-center, non-randomized, single arm, unblinded clinical study. [REDACTED]

[REDACTED] Up to 225 subjects will be enrolled world-wide. In the US, and Canada, up to 200 subjects will be enrolled to ensure 150 subjects are treated with an Arctic Front Advance Cardiac CryoAblation Catheter. The maximum number of subjects treated at Canadian centers combined is 45 subjects. Up to 25 subjects will be enrolled in Japan to ensure 15 subjects are treated with an Arctic Front Advance Cardiac CryoAblation Catheter. The maximum number of subjects treated at Japanese centers is 15 subjects.

6. Statistical Methods

6.1. Study Subjects

6.1.1. Disposition of Subjects

Subjects included in our primary analysis cohort require all of the following conditions: eligibility, consent to be studied, and treatment pulmonary veins with the Arctic Front Advance Cardiac Cryoablation Catheter System. The study will collect data on subjects who consented to be studied and to the cryoablation procedure, but who were given a different treatment at the time of operation, but these cases will not affect the analysis of primary, secondary, or ancillary objectives, as they do not meet the criteria of undergoing a cryoablation procedure.

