6.1.2. Clinical Investigation Plan (CIP) Deviations

Protocol deviations will be described using frequency tables and listings. As stated above in section 6.1.1, subjects will be excluded from analysis of primary, secondary, or ancillary endpoints if any of these conditions apply:

- Subject does not meet the study's entry criteria and exited prior to procedure
- Subject did not consent to the procedure
- Subject did not undergo a planned procedure with the Arctic Front™ Cardiac Cryoablation Catheter System.

Handling of visit window deviations as it affects the study's primary, secondary and ancillary endpoints is discussed further in section 6.2.

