6.1.3. Analysis Sets

=

The **Full analysis set** consists of all enrolled subjects who sign informed consent. The full analysis set will be used for AE reporting in general and ancillary objective [REDACTED]

The **Modified Intention-to-Treat (mITT)** cohort is the subset of subjects who maintain informed consent at least until the index cryoablation procedure was finished. For endpoints analyzed in this group of subjects, the standard Intention-to-Treat (ITT) protocol applies immediately upon insertion of the cryoballoon catheter into the subject's vasculature. The mITT cohort will be used in the analysis of the primary efficacy objective, the secondary objective regarding Quality of Life (QoL), and the ancillary objective [REDACTED]. The mITT dataset will be used in the analysis of the primary efficacy and safety objectives, as well as for the secondary objective and ancillary objectives [REDACTED].

This study has planned submissions to the US FDA and Japan PMDA. The Pre-Market Approval Submission (PMA-S) to the US FDA will include subjects from centers in US and Canada. If full 12-month data is available from Japan subjects at the time of PMA-S submission, the Japan data may be included in the PMA-S submission. The submission to the Japan PMDA will include analysis from data collected from all four geographies. The analyses for both submissions will follow the same pre-specified analysis procedures, so this SAP will not distinguish between the PMDA submission cohort (165 subjects expected) vs. the subset of subjects used for the PMA-S (150 subjects expected) except when differences due to sample size are relevant to the discussion.

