6.2.2.2. Endpoint Definition

Treatment success is defined as freedom from treatment failure. Treatment failure is defined as any of the following components:

- Acute procedural failure
- Documented AF/AT/ AFL on Holter/TTM/12-lead ECG after the 90 day blanking period
 - Minimum of 30 seconds on Holter/TTM and 10 seconds on 12-lead ECG
- A reablation for the treatment of recurrent AF/AT/AFL after the 90 day blanking period
- Class I or III antiarrhythmic drug (AAD) dose increase from the historic maximum ineffective dose (prior to the ablation procedure) or initiation of a new Class I or III AAD after the 90 day blanking period. Note: remaining on the same pre-ablation dose or decreased dose, or re-initiation of a previously failed or not tolerated Class I or III AAD after the 90 day blanking is not considered a failure. Subjects are allowed to remain on Class I or III antiarrhythmic medications at the historic maximum ineffective dose (on prior to the ablation procedure) after the 90 day post-procedure blanking period.
- Ablation using RF in the left atrium

Blanking period is defined as the first 90 days after the index ablation procedure. Recurrences of atrial arrhythmias during the blanking period will not be counted in the determination of the first clinical failure for the primary endpoint. Within the blanking period, recurrent arrhythmias can be managed with antiarrhythmic drugs, cardioversion or one cryo re-ablation procedure of the pulmonary veins. Titration of Class I and III antiarrhythmic medications are allowed during the blanking period.

Acute procedural failure is defined as:

- Inability to isolate all accessible targeted pulmonary veins (minimally assessed for entrance block and, where assessable, exit block) during the index procedure
- Left atrial non-PVI ablations including but not limited to, ablation of linear lesions, complex fractionated electrograms or non-PV triggers

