6.2.2.3. Analysis Methods

The probability of a subject achieving effectiveness success at 12 months (365 days) will be estimated using survival analysis, the Kaplan-Meier method. The standard error will be approximated using Greenwood's formula. A two-sided 95% log-log confidence interval for the probability will be constructed. For every treated subject, day 0 is defined as the day of the index cryoablation procedure. For subjects with treatment failure, the survival date will be set to the date of the treatment failure. For subjects without treatment failure through 12 months, those subjects will be censored at the last study contact date recorded on CRF which may include the last study visit, the exit date, or death date. If a subject without a treatment failure is lost to follow-up, the censoring date will be set to the last known study visit date.

For the component of the endpoint, documented AF/AT/AFL, if this documentation resulted from rhythm monitoring occurring at the 12-month visit within the 12-month visit window, the date of recurrence will be set to 365 days from the study ablation procedure so that these events will be counted as treatment failures in the 12-month Kaplan-Meier analysis. This objective will be analyzed in the mITT dataset: all enrolled subjects who have the Arctic Front Advance Cardiac CryoAblation Catheter inserted into vasculature will be included.

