6.2.2.5. Sensitivity Analyses

A sensitivity analysis will be conducted to estimate the potential impact of subjects with less than 12 months of follow-up at the final analysis, which is described in more detail in section 6.5.

In the event a subject is enrolled, treated, but later discovered they did not meet eligibility, a sensitivity analysis will be conducted to understand the impact of these subjects. The same analysis methods will be utilized as described in section 6.2.2.3, but those subjects not meeting eligibility will be excluded.

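### SAP 6.1.1 requires pulmonary-vein treatment for the primary analysis cohort, but the endpoint sections and the CIP require only catheter insertion

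*SAP*

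**What the plan says.** Four places in the SAP describe who is analysed.

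- **6.1.1, on disposition, reads:** "Subjects included in our primary analysis cohort require all of the following conditions: eligibility, consent to be studied, and treatment pulmonary veins". The treatment meant is cryoablation using the study's balloon system. A later sentence says data will also be collected on consented subjects "given a different treatment at the time of operation, but these cases will not affect the analysis of primary". That sentence names the other objectives as well. The reason given is that these subjects did not have a cryoablation procedure.
- **6.1.2, CIP Deviations:** cites 6.1.1 and lists exclusions. One is "Subject did not undergo a planned procedure with the Arctic Front" system. Another covers subjects who fail the study's "entry criteria and exited prior to procedure".
- **6.1.3, Analysis Sets:** defines the modified intention-to-treat (mITT) set by consent kept until the index procedure ended, and says the ITT "protocol applies immediately upon insertion of the cryoballoon catheter into the" subject's vasculature.
- **6.2.2.3 (efficacy) and 6.2.3.3 (safety):** both use the mITT set, described as "all enrolled subjects who have the Arctic Front Advance Cardiac CryoAblation Catheter inserted into vasculature will be included". CIP 17.3.1 and 17.3.2 give the same rule.

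On eligibility, SAP 6.2.2.5 says: "In the event a subject is enrolled, treated, but later discovered they did not meet eligibility, a sensitivity analysis will be conducted". It therefore treats such subjects as part of the primary analysis.

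**The concern.** The two rules part on one group: catheter inserted, no vein treated. An example is a procedure stopped after insertion for a complication, or a switch to another modality before any vein was frozen. SAP 6.1.1 leaves these subjects out; the endpoint sections and the CIP keep them in. A subject switched after some vein cryoablation is in under both.

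The direction matters because the study is single-arm and unblinded and is tested against fixed goals. SAP 6.2.2.2 counts "Inability to isolate all accessible targeted pulmonary veins" as acute procedural failure, and RF ablation in the left atrium as treatment failure. Most inserted-but-untreated subjects would therefore be failures, and leaving them out raises the success rate. For safety, leaving them out helps the device only if they have clearly more primary safety events than the rest.

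Two smaller conflicts sit alongside. Read literally, the eligibility condition in 6.1.1 contradicts 6.2.2.5, although the first bullet of 6.1.2 limits it to subjects who left before the procedure. The consent wording in 6.1.3 differs from the insertion rule only if consent is withdrawn during the procedure.

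**Working it through.** **The plan's own figures.** Exact one-sided binomial, inputs from SAP 7.1 and 7.2:

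| Test | N | Pass if | Alpha | Power |
|---|---|---|---|---|
| Efficacy, 40% vs 54% | 135 | ≥66 successes | 0.0224 | 0.899 |
| Efficacy, 40% vs 54% | 148 | ≥72 successes | 0.0202 | 0.917 |
| Safety, 13% vs 5% | 135 | ≤9 events | 0.0141 | 0.860 |
| Safety, 13% vs 5% | 148 | ≤11 events | 0.0233 | 0.932 |

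All four reproduce. They do not depend on the cohort wording.

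**The rules side by side**

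| Subject | SAP 6.1.1 | SAP 6.2.2.3, 6.2.3.3; CIP 17.3.1, 17.3.2 |
|---|---|---|
| Catheter never inserted | out | out |
| Inserted, no vein treated | **out** | **in** |
| Inserted, some vein cryoablation, then another modality | in | in |
| Treated, later found ineligible | out (literal reading) | in |

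The third bullet of 6.1.2 does not say whether insertion without ablation counts as undergoing the planned procedure.

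**Effect of one subject.** The analysis is Kaplan-Meier with Greenwood variance and a log-log 95% interval. Without censoring, with S the event-free proportion of n, the lower bound is S^exp(t), where t = 1.96 × √[(1−S)/(nS)] / |ln S|.

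- Efficacy, 72/150: S = 0.480, t = 1.96 × √(0.520/72)/0.734 = 0.227, lower bound 39.8%. Goal missed.
- Efficacy, 72/149 (one failure dropped): S = 0.483, t = 0.228, lower bound 40.1%. Goal met.
- Safety, 12/150 events: S = 0.920, upper bound on the event rate 13.7%. Goal missed.
- Safety, 11/149 (one subject with an event dropped): upper bound 12.9%. Goal met.

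At the planning rates, exactly 72 successes (at 54%) has probability 2.2% and exactly 12 safety events (at 5%) has probability 3.5%.

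**Type I error.** The untreated share q is not in the documents, so it is varied. The number dropped is K ~ Binomial(150, q).

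- Minimum successes to pass: 73 of 150, 72 of 149, 72 of 148, 71 of 147.
- Maximum safety events to pass: 11 of 150, 11 of 149, 10 of 148.
- The null holds in all inserted subjects, so success in the treated is (0.40 − q·s)/(1 − q), where s is the success rate among the untreated. With q = 1% and s = 0 this is 0.40/0.99 = 0.404.
- The event rate in the treated is (0.13 − q·f)/(1 − q), where f is the event rate among the untreated. With q = 1% and f = 0.5 this is 0.125/0.99 = 0.126.
- Type I error is the sum over K of P(K) × P(pass with 150 − K subjects).

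| | q = 0.5% | 1% | 2% | 5% |
|---|---|---|---|---|
| At least one such subject, 1 − (1−q)^150 | 53% | 78% | 95% | >99% |
| Efficacy, all untreated fail | 2.4% | 2.8% | 3.5% | 6.4% |
| Efficacy, 75% fail | 2.2% | 2.4% | 2.6% | 3.3% |
| Efficacy, all fail, 10% attrition (simulated) | 2.4% | 2.7% | 3.3% | 6.2% |
| Safety, a quarter have an event | 2.0% | 1.9% | 1.8% | 2.7% |
| Safety, half have an event | 2.2% | 2.3% | 2.7% | 7.2% |

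Under the insertion rule the values are 1.9% for efficacy (2.1% with attrition) and 2.0% for safety. The 75% row allows for subjects who might not count as failures because the definition is limited to accessible targeted veins. The attrition row uses 200,000 simulated trials per share: untreated subjects fail on day 0, other failures fall uniformly over days 91–365, and 10% are censored uniformly over the year. Some movement reflects discrete cut-offs; for example, the safety limit falls from 11 to 10 events between 149 and 148 subjects.

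**The case against.** The best defence is that the governing rule is already clear. The insertion rule stands in both endpoint sections of the SAP and both in the CIP, and 6.1.3 applies ITT from insertion. Section 6.1.1 is about disposition, and its term for the primary cohort is not one of the sets defined in 6.1.3. The documents also use the word treated loosely for the analysed population, so 6.1.1 might mean only subjects in whom the catheter was never used, which CIP 13.19 lists as an exit reason.

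The first part stands as a forecast: a programmer working from the endpoint sections would include these subjects. The reading of treatment as insertion does not stand, because 6.1.1 bases the exclusion on not having undergone cryoablation, and 6.1.2 carries it forward as an exclusion rule.

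The objection on size largely stands. The share is assumed and nothing in the documents supports 5%. At a 1% share and planning rates, the efficacy verdict changes in about 2.2% of trials if all untreated subjects fail. For safety, with a quarter having an event, it changes toward success in 0.9% and toward failure in 1.0%, so there is no clear direction.

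SAP 6.8, which reports no change to the CIP's principal features, supports the insertion rule less directly than it seems. It refers to CIP version 5, once under another study's name, and the CIP at hand is version 6. The version 6 change log lists no change to the analysis population, so the inference is reasonable.

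**Conclusion.** The SAP contains two incompatible rules for the primary analysis set, and nothing in either document ranks them. The contradiction is certain from the text. Its numerical effect is conditional on the untreated share, which is assumed.

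For efficacy, the 6.1.1 rule favours the device: at a 1% share it takes type I error to 2.4–2.8%, depending on how many such subjects fail, against 1.9% under the insertion rule and 2.5% nominal. It becomes material only at shares of 2% or more with nearly all failing. For safety at a 1% share the error stays at 1.9–2.3%; it exceeds nominal only at larger shares, most clearly if half of these subjects have an event.

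The text should be corrected even though the effect is probably small. At a 1% share there is a 78% chance of at least one such subject among 150, and the choice between the rules would then be open after outcomes are known.

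**What to change.** - Restate 6.1.1 and the third bullet of 6.1.2 so that the primary analysis set (mITT) is every enrolled subject with the Arctic Front Advance catheter inserted into the vasculature, whether or not a vein was treated, another modality was used, or ineligibility was found later.
- Define mITT in 6.1.3 by the same rule, replacing the wording on consent to the end of the procedure.
- Keep removal of ineligible subjects only as the 6.2.2.5 sensitivity analysis.
- Report the number inserted but untreated, with their efficacy and safety outcomes, and state how they are scored under the acute procedural failure definition.

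The cost is SAP wording only. Sample size and power do not change. Estimates may be slightly less favourable than under 6.1.1.

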6.1.2. Clinical Investigation Plan (CIP) Deviations

Protocol deviations will be described using frequency tables and listings. As stated above in section 6.1.1, subjects will be excluded from analysis of primary, secondary, or ancillary endpoints if any of these conditions apply:

- Subject does not meet the study's entry criteria and exited prior to procedure
- Subject did not consent to the procedure
- Subject did not undergo a planned procedure with the Arctic Front™ Cardiac Cryoablation Catheter System.

Handling of visit window deviations as it affects the study's primary, secondary and ancillary endpoints is discussed further in section 6.2.

